7 STUDY RISKS AND BENEFITS

7.1 POTENTIAL RISKS AND MANAGEMENT

CPET with incremental and constant work load are part of the usual pulmonary rehabilitation programme tests. High flow nasal oxygen and exercise capacity assessment are commonly used in patients with interstitial lung diseases both, when stable and during exacerbations. Only stable patients will be part of this study. The tests will be monitored and stopped if any of the following occurs:

Progressive Chest Pain.

Oxygen desaturation to below 80%.

Hypotension, drop in systolic blood pressure or failure of BP to rise through exercise.

Severe Hypertension (>250/120 mmHg).

More than 2mm ST segment depression (horizontal or negative sloping).

3mm ST depression (positive sloping).

Progressive ST Segment elevation.

AV Block.

Frequent Ventricular Ectopic or Ventricular Arrhythmias.

Rapid Supra-ventricular Arrhythmias.

All aforementioned are test termination criteria and we have everything necessary to provide emergency care and stabilize the patient if this is needed.

7.2 POTENTIAL BENEFITS

The results of the assessments will be sent to their usual care provider if they wish. Any abnormalities found during the assessments, including of initial screening, will be reported to the general practitioner of the patient. The results of the study may help to identify a strategy to improve the delivery of pulmonary rehabilitation to patients with ILD with a potential to improve the effects of pulmonary rehabilitation in this population.

9. PROJECT MANAGEMENT AND QUALITY ASSURANCE

The project team, consisting of a grant holder and research staff, will meet twice monthly. There will be a weekly meeting between the lead researcher and his collaborators to discuss the progress of the study.

10 OVERSIGHT ARRANGEMENTS

10.1 INSPECTION OF RECORDS

Investigators and institutions involved in the study will permit trial related monitoring and audits on behalf of the sponsor, REC review, and regulatory inspection(s). In the event of audit or monitoring, the Investigator agrees to allow the representatives of the sponsor direct access to all study records and source documentation. In the event of

regulatory inspection, the Investigator agrees to allow inspectors direct access to all study records and source documentation.

10.2 STUDY MONITORING AND AUDIT

The ACCORD Sponsor Representative will assess the study to determine if an independent risk assessment is required. If required, the independent risk assessment will be carried out by the ACCORD Quality Assurance Group to determine if an audit should be performed before/during/after the study and, if so, at what frequency.

Risk assessment, if required, will determine if audit by the ACCORD QA group is required. Should audit be required, details will be captured in an audit plan. Audit of Investigator sites, study management activities and study collaborative units, facilities and 3rd parties may be performed.

11. GOOD CLINICAL PRACTICE

11.1 ETHICAL CONDUCT

The study will be conducted in accordance with the principles of the International Conference on Harmonisation Tripartite Guideline for Good Clinical Practice (ICH GCP).

Before the study can commence, all required approvals will be obtained and any conditions of approvals will be met.

11.2 INVESTIGATOR RESPONSIBILITIES

The Investigator is responsible for the overall conduct of the study at the site and compliance with the protocol and any protocol amendments. In accordance with the principles of ICH GCP, the following areas listed in this section are also the responsibility of the Investigator. Responsibilities may be delegated to an appropriate member of study site staff.

11.2.1 Informed Consent

The Investigator is responsible for ensuring informed consent is obtained before any protocol specific procedures are carried out. The decision of a participant to participate in clinical research is voluntary and should be based on a clear understanding of what is involved.

Participants must receive adequate oral and written information – appropriate Participant Information and Informed Consent Forms will be provided. The oral explanation to the participant will be performed by the Investigator or qualified delegated person, and must cover all the elements specified in the Participant Information Sheet and Consent Form.

The participant must be given every opportunity to clarify any points they do not understand and, if necessary, ask for more information. The participant must be given

sufficient time to consider the information provided. It should be emphasised that the participant may withdraw their consent to participate at any time without loss of benefits to which they otherwise would be entitled.

The participant will be informed and agree to their medical records being inspected by regulatory authorities and representatives of the sponsor(s).

The Investigator or delegated member of the trial team and the participant will sign and date the Informed Consent Form(s) to confirm that consent has been obtained. The participant will receive a copy of this document and a copy filed in the Investigator Site File (ISF) and participant's medical notes (if applicable).

11.2.2 Study Site Staff

The Investigator will be familiar with the protocol and the study requirements. It will be investigator's responsibility to ensure that all staff assisting with the study are adequately informed about the protocol and their trial related duties.

11.2.3 Data Recording

The Principal Investigator will be responsible for the quality of the data recorded in the CRF at each Investigator Site.

11.2.4 Investigator Documentation

The Principal Investigator will ensure that the required documentation is available in local Investigator Site files ISFs.

11.2.5 GCP Training

All the research personnel involved in the study have undertaken GCP training in order to understand the principles of GCP.

11.2.6 Confidentiality

All laboratory specimens, evaluation forms, reports, and other records will be identified in a manner designed to maintain participant confidentiality. All records will be kept in a secure storage area with limited access. Clinical information will not be released without the written permission of the participant. The Investigator and study site staff involved with this study may not disclose or use for any purpose other than performance of the study, any data, record, or other unpublished information, which is confidential or identifiable, and has been disclosed to those individuals for the purpose of the study. Prior written agreement from the sponsor or its designee will be obtained for the disclosure of any said confidential information to other parties.

11.2.7 Data Protection

All Investigators and study site staff involved with this study comply with the requirements of the appropriate data protection legislation (including the General Data

Protection Regulation and Data Protection Act) with regard to the collection, storage, processing and disclosure of personal information. Computers used to collate the data will have limited access measures via user names and passwords. Published results will not contain any personal data and be of a form where individuals are not identified and re-identification is not likely to take place.

12. STUDY CONDUCT RESPONSIBILITIES

12.1 PROTOCOL AMENDMENTS

Any changes in research activity, except those necessary to remove an apparent, immediate hazard to the participant in the case of an urgent safety measure, will be reviewed and approved by the Chief Investigator.

Amendments will be submitted to a sponsor representative for review and authorisation before being submitted in writing to the appropriate REC, and local R&D for approval prior to participants being enrolled into an amended protocol.

12.2 MANAGEMENT OF PROTOCOL NON COMPLIANCE

Prospective protocol deviations, i.e. protocol waivers, will not be approved by the sponsors and therefore will not be implemented, except where necessary to eliminate an immediate hazard to study participants. If this necessitates a subsequent protocol amendment, this should be submitted to the REC, and local R&D for review and approval if appropriate.

Protocol deviations will be recorded in a protocol deviation log and logs will be submitted to the sponsors every 3 months. Each protocol violation will be reported to the sponsor within 3 days of becoming aware of the violation. All protocol deviation logs and violation forms will be emailed to [contact]

Deviations and violations are non-compliance events discovered after the event has occurred. Deviation logs will be maintained for each site in multi-centre studies. An alternative frequency of deviation log submission to the sponsors may be agreed in writing with the sponsors.

12.3 SERIOUS BREACH REQUIREMENTS

A serious breach is a breach which is likely to effect to a significant degree:

- (a) The safety or physical or mental integrity of the participants of the trial; or
- (b) The scientific value of the trial.

If a potential serious breach is identified by the Chief investigator, Principal Investigator or delegates, the co-sponsors ([contact]) will be notified within 24 hours. It is the responsibility of the co-sponsors to assess the impact of the breach on the

scientific value of the trial, to determine whether the incident constitutes a serious breach and report to research ethics committees as necessary.

12.4 STUDY RECORD RETENTION

All study documentation will be kept for a minimum of 3 years from the protocol defined end of study point. When the minimum retention period has elapsed, study documentation will not be destroyed without permission from the sponsor.

12.5 END OF STUDY

The end of study is defined as the last participant's last visit. The Investigators or the co-sponsor(s) have the right at any time to terminate the study for clinical or administrative reasons. The end of the study will be reported to the REC, and R+D Office(s) and co-sponsors within 90 days, or 15 days if the study is terminated prematurely. The Investigators will inform participants of the premature study closure and ensure that the appropriate follow up is arranged for all participants involved. End of study notification will be reported to the co-sponsors via email to [contact]. A summary report of the study will be provided to the REC within 1 year of the end of the study.

12.6 INSURANCE AND INDEMNITY

The co-sponsors are responsible for ensuring proper provision has been made for insurance or indemnity to cover their liability and the liability of the Chief Investigator and staff.

The following arrangements are in place to fulfil the co-sponsors' responsibilities:

- The Protocol has been designed by the Chief Investigator and researchers employed by the University and collaborators. The University has insurance in place (which includes no-fault compensation) for negligent harm caused by poor protocol design by the Chief Investigator and researchers employed by the University.
- Sites participating in the study will be liable for clinical negligence and other negligent harm to individuals taking part in the study and covered by the duty of care owed to them by the sites concerned. The co-sponsors require individual sites participating in the study to arrange for their own insurance or indemnity in respect of these liabilities.
- Sites which are part of the United Kingdom's National Health Service will have the benefit of NHS Indemnity.
- Sites out with the United Kingdom will be responsible for arranging their own indemnity or insurance for their participation in the study, as well as for compliance with local law applicable to their participation in the study.

13 REPORTING, PUBLICATIONS AND NOTIFICATION OF RESULTS

13.1 AUTHORSHIP POLICY

Ownership of the data arising from this study resides with the study team.

Appendix A

Cardiopulmonary Exercise Test specifications and SOP

Two operators will be present during the test. If the patient has cardiac issues or other clinical conditions which may be of concern then a doctor will be present.

Before booking the appointment, ensure supervising doctor is available if appropriate.

Equipment Setup

Before patient testing, prepare the following;

- Mouthpiece for spirometry
- Serial sheet for spirometry
- CPET data sheet (located in the top drawer under the fridge)
- Mask (prepare a range of sizes)

- Flow head (located in plastic box on shelf on right of door)
- White ring adapter (located as above)
- ECG box (located as above)
- ECG electrodes (located in cupboard above the left of the sink)
- Skin prep pads (located as above)
- Ensure there is paper in the printer and the flap below is pulled out to catch it
- Ensure fan in room
- Print the patient referral (go to workbench on Trak, highlight patient + select print at the top of the page)
- Check if the patient has been before – if they have the patient should be tested at the same wattage

To Start System

Open gas cylinder and ensure adequate gas and pressure

Turn on system by pressing button on bottom right of the right hand monitor

Double click on “Breeze” icon on left hand screen to open program

Enter Login Name and Password and press “OK”

Ensure vacuum pump is on. If not, press “Vac” at the top of the screen (if the timer is stuck at 30:00, the vacuum pump is probably off)

Turn on the bike using the switch at the back below the seat

Calibration

Press “Calibrate” at the top of the screen

Take the 3L syringe from below the left hand side of the desk and attach the flow head to the blue rubber end with the side containing the holes facing into the syringe

Connect the umbilicus to the top of the flow head

Press “zero flow”

Press “start”

Withdraw and inject as directed until “calibration successful” is displayed

Replace the umbilicus to the port with the patterned side up

Remove the flow head and replace the syringe

Press the “O2 and CO2 analysers” tab

Click “calibrate” and wait until “calibration successful” is displayed

Click “OK” at the bottom left of the screen

Patient Details

For Existing Patients-

Click on yellow folder (Open Patient) to search for the patient.

Select Find.

Click on the drop down menu for search options, i.e. Name, ID etc.

Enter the search option selected to search for the patient.

If the patient is found it is highlighted.

Select Open and then add visit

Enter patient demographics and history as necessary.

Ensure that “GX Predicted Set Selection” has the option “Glaser” selected

For New Patients-

Search first as above, if not found, close that window.

Click on White folder (new Patient)

Enter all patient details.

Then select Add Visit.

Enter more details as necessary (Height, Weight, Requesting Physician/Unit, Site and Physiologist are Mandatory)

Ensure that “GX Predicted Set Selection” has the option “Glaser” selected

The Patient History tab should be used to enter more details, e.g. medication and clinical details, smoking history etc.

To close any patient demographic window, click on the yellow open folder to close.

Preparing the Patient

Check patient details and measure height and weight (NB Maximum weight for bike is 160kg).

Check with patient for any contraindications to testing.

Contraindications for Testing

- Recent/Acute M.I
- Unstable Angina
- Chest Pain
- ST depression > 2mm on resting ECG in most leads
- Uncontrolled hypertension at rest (>180/100 mmHg)
- Uncontrolled arrhythmias
- Severe Aortic Stenosis
- SpO₂ < 80% at rest

Perform SVC and FVC manoeuvres as per SOP in section 3 folder. A white ring adapter is required to connect the flow head to the mouthpiece. If the spirometry was performed on box, predicted values must be refreshed – Click edit, then “rerun predicted values”.

Fill in the CPET data sheet, including the predicted HR_{max} (220-age) and predicted V_{emax} (40 x FEV₁).

Explain the test to the patient, e.g. “You are going to be doing a bicycle exercise test but we are going to monitor several things whilst you exercise. You will have electrodes on your chest to monitor your heart, a blood pressure cuff on your arm for your blood pressure, a small clip on your ear lobe to monitor your oxygen saturation and a face mask which will measure your breathing pattern and oxygen consumption. We will get you on the bicycle first, just breathing for 1 minute before we start you exercising and then there will be a warm up period of 3 minutes easy pedalling before we start increasing the workload as though you were going up a hill. We want you to really push yourself and do as much as possible.”

Prepare earlobe with a vasodilator cream for pulse oximeter probe.

Stickers (called electrodes) and a band will be put onto the chest of the patients by themselves to monitor their heart rate and rhythm, therefore, their privacy will be ensured. Some men may need to have a small area of their chest shaved in order for the electrodes to stick to the skin. Seat patient on bike.

Check height of bike and adjust as necessary using the up and down arrows on the bike unit until the patient’s extended leg has a slight bend at the knee. The handlebars can also be adjusted by loosening the black handles on handlebar unit. (If the screen displays a menu, select PC Mode)

Attach ear probe for oximetry and run the cable over the hook on the back wall to ensure it stays out the way.

Fit the blood pressure cuff by feeling for the brachial pulse and fitting the orange tab over it, 2-3cm above the cubital fossa. Secure the cable through the Velcro on the handlebars.

Fit mask over the patient's face. To ensure no leaks, instruct the patient to breathe in maximally then cover the hole in the mask with the palm of your hand as they exhale. Repeat with patient inhaling against the palm of your hand.

Establish appropriate workload for patient (CF patients are all tested at 25W).

Wasserman Equations for Predicted Work Rate Increment

- Unloaded VO₂ = (150 + (6 x weight in kg))
- VO₂ Peak = (height in cm – age) x 14 for females, x 20 for males
- Predicted Work Rate Increment = VO₂ Peak - Unloaded VO₂

Patient Testing

Click the “GX” tab at the bottom of the screen

Under “Script Name”, select “JAI”

Select the desired work rate increment by choosing the appropriate ramp under “default protocol”

Ensure that “Borg Scale” is selected to “6-20”

Click on “summary” to gain a value for VO₂ Max and write this on the CPET data sheet

Select the “test” tab at the bottom of the screen

Turn on SpO₂ monitor

Ensure the umbilical is connected to the black port located below the screen to the left and click “Gas AutoCal”.

Then plug the umbilical into the flow head and strap it over the patients head onto the headpiece

Click on the ECG icon on the right hand computer screen

Turn on the ECG box by pressing the button on the front of box

Observe the ECG

Press **Start**

Keep patient still on the bike

Take a resting BP measurement by pressing the red droplet with a circle inside

Record resting BP along with SpO2 and HR on the CPET data sheet

Click on ECG event icon

Change Mason-Likar to “interpret all”

Monitor resting ECG for any abnormalities

Press **Exercise**

Instruct the patient to begin pedalling at 70 rpm

Take a baseline BP measurement by pressing the red droplet with a circle inside

Record baseline BP along with SpO2 and HR on the CPET data sheet

After three minutes, tell the patient that the workload will begin to increase

The system will automatically take BP measurements approximately every 3 minutes – these must be recorded along with SpO2 and HR on the CPET data sheet

Encourage the patient throughout to perform maximally

Observe all parameters throughout, especially the ECG for ST depression or arrhythmias, but also to pick up any erroneous measurements arising from technical factors e.g. low VO2 from a leak etc.

Terminate the test if the patient fulfils any of the termination criteria;

Termination Criteria

- Maximal test – patient could not do any more
- Progressive Chest Pain
- Oxygen desaturation to below 80%
- Hypotension, drop in systolic blood pressure or failure of BP to rise through exercise.
- Severe Hypertension (>250/120 mmHg)
- More than 2mm ST segment depression (horizontal or negative sloping)
- 3mm ST depression (positive sloping)
- Progressive ST segment elevation

- AV Block
- Frequent Ventricular Ectopic or Ventricular Arrhythmias
- Rapid Supra-ventricular Arrhythmias

Press **Recovery**

Click recovery as soon the patient stops

Take a BP at beginning of recovery, and every three minutes until baseline HR and SpO₂ values are reached again

Press **Stop**

Ask the patient what made them stop the test and record on the CPET data sheet

Give the patient a Borg Score scale for perceived exertion and record on CPET data sheet

Click on ECG icon to stop ECG

Turn off ECG by pressing the button on the box

Printing Results

ECG

Click “page review”

Deselect ectopic etc. unless you want to print an example of something specific

Press the running man icon at the top of the right hand screen

Press “preview”

At the top left of the left hand screen, deselect all tick boxes except “exam summary”, “rate/BP/workload trends” + “peak averages”

Click “refresh” at the bottom left of the screen

Click the “X” at the top right of the screen

Click “save” and then “exit”

Click the save icon on the right hand screen

AT

Click the AT tab at the bottom right of the screen

Move the AT line to the correct position

To view other graphs press F12

Click “save”

Print

Select Quick Print from menu bar at top of screen

Select “JAI Report”

Cleaning

Place ECG electrodes in the domestic waste bin

Wipe down;

- Bike
- BP cuff
- SpO2 sensor
- ECG box

Clean in the basin located under the sink with hot, soapy water;

- Mask
- Flow head
- Headgear

Hang the headgear from the hooks on the back wall

Prepare descogen by filling the appropriate lidded container with water and adding one scoop of descogen and place the mask and flow head in. Leave for 20 minutes then rinse and place on the side to dry

Closing down the System

Close the patient

Exit the program

Shut down the computer

Close the gas cylinders

Turn off the bike using the switch at the back

Reviewing Results

Open patient file to be reviewed.

Highlight date of tests to be reviewed and select Open visit.

Click on tab to review particular test results.

To see graphical display for test results, highlight the test time

Reviewing Reports

Open patient file to be reviewed.

Highlight date of tests to be reviewed and select Open visit.

Select Quick print from top menu bar.

Select Report switchboard.

Select appropriate report, e.g. JAI report

Select Preview to display the report

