In addition, a Cardiopulmonary Exercise Test (CPET) will be carried out.

Furthermore, a Constant work rate Cycle Test at 75% of peak work rate (obtained from a maximal exercise test conducted beforehand) will be carried out. The participants will be able to rest for about 20 minutes between each test and we will offer them refreshments.

Physical activity levels in daily life will also be measured using Actigraph GT3x activity monitor, which will be delivered during the baseline appointment to use in their house for only 1 week before and 1 week after of the intervention, this is a belt that the participants will have to use like any other. After of the intervention they should return it to us during their post intervention appointment.

Moreover, two questionnaires called St George's Respiratory Questionnaire (SGRQ) and the Hospital Anxiety and Depression Scale (HADS), will have to be answered to measure the quality of life and anxiety and depression levels respectively. These test will be answered at home.

During the first day after of the intervention, participants will be undergone exactly to the same tests as in the baseline appointment, except height.

Intervention, a group of participants will be submitted to 8 weeks of a PR program based on HIIT plus HFNO and the other group will also be submitted to 8 weeks of a PR program based on HIIT but with conventional oxygen delivery without HFNO. Both HIIT will be performed at the same workload, which will be progressive throughout the 8 weeks and will be modified during each session. Starting with high load intervals at 60% of the maximal watts achieved beforehand during a maximal CPET divided by lower load intervals at 40% maximum load during the first week, and finishing with high load intervals at 110% maximum load separated by load intervals at 80% maximum load in the last weeks. Basically the participants will have to pedal in a stationary bicycle for 30 minutes (aerobic training), during the other 20 minutes the patients will do exercises for their upper limbs using Thera bands and dumbbells (strength training). Muscles of upper limbs to work will be deltoids, pectorals and biceps (3 series of 10 repetitions each). Finally the participants will receive 10 minutes of respiratory physiotherapy including techniques to eliminate phlegm, breathing exercises and ludic activities to train the respiratory muscles such as inflating balloons.

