4.4 EXCLUSION CRITERIA

1. - Emphysema greater than extent of fibrosis on high resolution computed tomography (HRCT) of the thorax.
2. - FEV1/FVC ratio < 70%.
3. - Participants should not be taking part in other interventional studies currently. Our research is not a CTIMPs and co-enrolment will not be allowed under any circumstances.
4. - Absolute contraindications for cardiopulmonary exercise testing, which are:
 - a. - Unstable angina
 - b. - Uncontrolled arrhythmias causing symptoms or hemodynamic compromise.
 - c. - Syncope.
 - d. - Active endocarditis.
 - e. - Acute myocarditis or pericarditis.
 - f. - Symptomatic severe aortic stenosis.
 - g. - Uncontrolled heart failure.
 - h. - Acute pulmonary embolus or pulmonary infarction.
 - i. - Thrombosis of lower extremities.
 - j. - Suspected dissecting aneurysm.
 - k. - Uncontrolled asthma.

- l. - Pulmonary edema.
- m. - Room air desaturation at rest $\leq 85\%$
- n. - Respiratory failure.
- o. - Acute no cardiopulmonary disorder that may affect exercise performance or be aggravated by exercise (i.e. infection, renal failure, thyrotoxicosis)
- p. - Mental impairment leading to inability to cooperate.

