4.11 DURATION OF THE STUDY

In general, the study will consist of 8 weeks of intervention plus 1 day of evaluations before and after the intervention. The window between the baseline appointment and the first day of the intervention can be from 1 to 30 days, and the window between the last day of intervention and the post intervention appointment will be from 8 to 38 days.

Assessment	Screening	Baseline Appointment	To be done at home	Intervention (8 weeks)	Post-Intervention Appointment
-------------------	-----------	----------------------	--------------------	----------------------------	-------------------------------

		(1 st day before Intervention)	(Pre &Post Intervention)		(1 st day after Intervention)
Assessment of eligibility criteria	X				
Written informed consent	X				
Demographic data, contact details	X				
Randomisation	X				
Weight		X			X
Height		X			
Blood Test		X			X
Blood Pressure		X			X
QMVCT		X			X
mMRC		X			X
CPET		X			X
CWRCT		X			X
Physical activity levels in daily life			X		
SGRQ (Questionnaire)			X		
HADS (Questionnaire)			X		
Intervention 1 st Group HIIT + HFNO				X	
Intervention 2 nd Group HIIT + NC				X	

Observation: There will be continual ECG monitoring during all the tests.

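### Section 4.4 makes room-air resting SpO2 of 85% or below an absolute bar to exercise testing, but the operators' lists in Appendices A and B bar only values below 80%, on an unstated breathing gas

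*Protocol*

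**What the plan says.** Protocol Section 4.4 (Exclusion criteria), item 4, is introduced as "Absolute contraindications for cardiopulmonary exercise testing". Sub-item m under it is "Room air desaturation at rest", with the limit set at 85% or below.

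Appendix A (CPET) tells operators: "Check with patient for any contraindications to testing". The list that follows has a single saturation entry, "SpO₂ < 80% at rest". Appendix B (constant work rate test) carries the same instruction and the same entry. Neither names the breathing gas.

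The Section 4.11 schedule places "Assessment of eligibility criteria" in the screening column only. For the visit after training, Section 4.1 states that "participants will be undergone exactly to the same tests as in the baseline appointment, except height", so both exercise tests are repeated. Section 4.7 provides nasal-cannula oxygen at the assessment visits when needed, titrated to an SpO2 of at least 88%.

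**The concern.** Item 4m sits among the exclusion criteria, but its parent heading describes contraindications to the test itself. A contraindication to a test does not lapse once screening is over. The operator on the test day is nevertheless pointed to an appendix list with a lower limit and no stated gas. A patient whose resting saturation has fallen since screening could therefore be unfit for testing under Section 4.4 and still pass the list in the operator's hands.

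At stake is the clarity of a safety rule for tests in patients selected because they desaturate on exercise. One of the two tests, the constant work rate test, also yields the primary outcome (Section 3.1).

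**Working it through.** There is no plan figure to reproduce. The check is a comparison of texts with a little counting.

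1. **The two limits.** Section 4.4, item 4m: testing barred at SpO2 ≤ 85%, room air. Appendices A and B: testing barred at SpO2 < 80%, gas not stated. The cut-points differ by 85 − 80 = 5 points.

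2. **Values on which the lists disagree, assuming both are read on room air.** Item 4m bars 85% and below; the appendices allow 80% and above. The overlap is 80% to 85% inclusive: 85 − 80 + 1 = 6 whole-percent values.

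3. **If the appendix reading is taken on oxygen.** Section 4.7 allows oxygen at these visits, so this is possible. A patient with a room-air value below 80% could then also pass the appendix list. The disagreement widens.

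4. **Which tests are covered.** Item 4's heading names cardiopulmonary exercise testing, so the conflict with Appendix A is direct. For Appendix B it depends on Section 7.1, which speaks of "CPET with incremental and constant work load" and so treats both tests as CPET. Elsewhere (the abbreviations list, Section 4.7, the schedule) the two tests are listed separately, so this second step is an inference.

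5. **When the conflict can bite.** Section 4.8 has eligibility confirmed before randomisation, and randomisation before baseline procedures. At that point item 4m should keep out anyone at 85% or below. What remains is a fall in saturation between screening and baseline, or between baseline and the repeat tests. From the Section 4.11 windows, the baseline-to-repeat interval runs from about 1 + 56 + 8 = 65 days to 30 + 56 + 38 = 124 days, taking the 8 weeks as 56 days.

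6. **Whether any other text settles it.** Oxygen titration (Section 4.7), withdrawal by the investigator and stopping for exacerbation, inability to perform the test or disease progression (Section 4.6), and a doctor's attendance where there is clinical concern (Appendices A and B) all lower the risk. None of them sets a resting saturation below which a test must not start.

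**The case against.** The strongest defence is that the lists are cumulative. Section 4.4 governs entry, while the appendices are laboratory procedures for the test day. Appendix A is visibly a general document: it includes a workload rule for cystic fibrosis patients and omits several Section 4.4 items. A patient must clear both lists, and a short checklist does not override an exclusion. The two limits may also measure different things, one on room air and the other possibly on oxygen.

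Part of this stands. At enrolment the stricter limit governs, and the origin of the appendix text may explain the mismatch. It does not remove the conflict. Item 4's own heading makes the limit one on testing, eligibility is not scheduled again before the repeat tests, and operators are sent to the appendix list. If a lower on-oxygen floor was intended for the test day, the protocol does not say so.

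Two stronger readings are tempting and should not be drawn:

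- A reader might infer a fault from the start limit equalling the in-test stop ("Oxygen desaturation to below 80" per cent). Declining to start a test in someone who already meets its stopping rule is coherent.
- A reader might infer that a patient could begin within a point of mandatory termination. That ignores Section 4.7, under which such a patient would be given oxygen towards 88% or above.

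It is also fair to object that a stricter test-day limit can cost post-intervention endurance times in the sickest patients of a trial of about 30. That is a real cost of the remedy and has to be handled openly.

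**Conclusion.** The inconsistency is real and minor. The protocol states an absolute contraindication at 85% or below on room air, then gives operators a list that stops only below 80% on an unspecified gas. The mismatch is certain for the CPET in Appendix A. For the constant work rate test in Appendix B it holds if Section 7.1 is taken to class both tests as CPET.

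On the assumption that both limits refer to room air, it covers six whole-percent values. It can matter only for patients who deteriorate after screening, and existing provisions reduce that exposure. How many patients would be affected cannot be worked out from the document.

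A reader might go further and suspect bias between the arms or a distorted primary comparison. The protocol does not support that: the same lists apply to both arms, and nothing in it shows that patients in the disputed range would be distributed unequally.

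**What to change.** In the contraindication lists of Appendices A and B, replace "SpO₂ < 80% at rest" with: *SpO2 of 85% or below at rest on room air (Section 4.4, item 4m)*. Add one sentence saying that this is checked before each CPET and each constant work rate test, at baseline and after the intervention. Leave the in-test stop at below 80% as it is. Record, and report by arm, any patient not tested for this reason.

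The cost is one line in each of two appendices plus that sentence. Operators already record resting SpO2 before exercise, so the extra work is a short room-air reading. The downside is that a few deteriorated patients may have no post-intervention endurance time. Because that missingness would be related to outcome, the count and reason by arm should be reported with the primary result.
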